## 7.0 DURATION OF THERAPY

### 7.1 BCG

- Patients will receive within either 6 weeks of bladder biopsy or within 3 months of bladder biopsy and a cystoscopy within 6 weeks of enrollment confirming no visible tumor a 6 week course of BCG as described above.
- Please see section 10 for dosing delays and modifications. Patients unable to complete an induction course of BCG will be removed from the study and replaced with a new subject. The removed subject will be offered alternative treatment options.
- After completion of a 6 week course of BCG, patients will undergo a 2 week rest period before initiating sunitinib
- All patients will be assessed at 3 months after enrollment with repeat bladder biopsy done at the study institution and urine cytology regardless of completion of the study drugs as this is standard of care.
- Patients demonstrating residual disease at 3 months will receive a second complete cycle of the study drugs (BCG followed by sunitinib) if the tumor remains non-muscle invasive. However, patients may elect to proceed to alternative treatments if there is residual non-muscle invasive disease. Patients completing at least one cycle of the study treatment will be assessed for primary and secondary endpoints where applicable.
- Patients with evidence of muscle invasive disease on restaging bladder tumor biopsy will be withdrawn from the study and offered standard alternative treatment options.
- Any patients with a complete response to BCG followed by sunitinib at 3 months or 6 months will be placed on maintenance BCG therapy which is the current standard of care. The maintenance BCG schedule is outlined in Calendar 2. Calendar 2 represents an idealized version of maintenance therapy and actual maintenance therapy varies according to individual physician practice pattern. As such, we will recommend that patients follow the study calendar but the actual administration will be at the discretion of the treating physician based on practice pattern and medical decision making. In addition, surveillance cystoscopy and history and physical is dictated by maintenance schedule and will ultimately be at the discretion of the treating physician. Records of each maintenance treatment (dose, timing, and delays), surveillance, cystoscopy, history and physical, urine studies, imaging, and pathologic data (if obtained) will be collected by the study coordinator and documented for a total of 2 years following completion of the initial or second induction course of BCG to assess for treatment response. Please see section 10 for dose modification and reduction.

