### 4. Schedule:

Patients will receive intravesical BCG ( 50mg TICE BCG in 50 ml normal saline) once weekly for 6 weeks within 6 weeks of bladder biopsy confirming high risk non-muscle invasive urothelial carcinoma. Two weeks after completion of BCG, patients will receive Sunitinib (50 mg daily) continuously for 28 days followed by a two week rest period. Patients will be reassessed with transurethral resection and urine cytology. Those with residual/recurrent

disease will receive a second course identical to the initial protocol. Those with a complete response following initial or second treatment will be placed on maintenance BCG (3 week course every 6 months for 2 years). Those failing (progression, intolerance) initial/secondary treatments will be offered alternative therapy.

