### 4.4 ELECTROCARDIOGRAM. (within 3 months of registration)

### 4.5 MUGA SCAN (within 6 weeks of study enrollment)

## 5.0 REGISTRATION PROCEDURES

### 5.1 GENERAL GUIDELINES

Eligible patients will be recruited from the University of Michigan, Department of Urology Clinics. Patients signing informed consent and meeting eligibility criteria will be registered on study by the Study Coordinator. Once registration is complete, the registrar will provide the registering individual a study subject identification number.

Following registration, patients should begin protocol treatment within 3 weeks. Issues that would cause treatment delays should be discussed with the Principal Investigator.

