## 9.0 DURATION OF FOLLOW-UP

- Patients will be followed by study calendar
- the clinical course of all patients will be followed for a total of 2 years following completion of 1st or 2nd induction course of the study therapy.

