## 13.0 STUDY CALENDAR:

[name], Phase II Study of BCG followed by Sunitinib for High risk NMIBC

		Week 1-6 BCG Course 1		Week 8-12† Sunitinib cycle 1			TURBT or bladder biopsy	Therapeutic Plan			
Required studies	Pre-study	Week1	Week 6	Week 8	Week 10	Week 12	Week 14	1. Residual/Recurrent disease without progression: a. Negative MUGA scan-if positive, proceed to 3. b. 2 nd cycle of BCG followed by sunitinib (as per week 1-14) c. alternative treatment plan per treating clinician 2. No residual disease (Calendar 2): patient will proceed to maintenance BCG therapy per institutional standard a. alternative therapy may be chosen on maintenance at patient/physician discretion 3. Disease progression or patient/clinician desire: proceed to alternative treatment per standard of care			
PHYSICAL											
History and Physical	x			x	x	x					
ECOG performance status	x			x	x	x					
Medication check	x			x	x	x					
Toxicity assessment											
LABORATORY/ STUDIES											
CBCPD	x			x	x	x					
Comprehensive panel	x			x		x					
Magnesium				x		x					
EKG	x										
Dipstick Urine		x	x								
Urine cytology*	x						x				
PT/PTT	x					x					
TSH	x										
MUGA Scan	x										
SPECIMEN SAMPLES											
Urine*		x 	x 	x		x	x				
Bladder biopsy							x				
Serum		x 	x 	x		x					
X-RAYS AND SCANS											
Chest radiograph	x										
CT or MRI abdomen/ pelvis or IVP	x										
Cystoscopy or report confirming eligibility	x										
Drug: Sunitinib				x							
Dispense BP log, Study drug info, and medication diary				x							

\* voided urine cytology obtained in clinic, instrument urine cytology obtained in operating room

† Medical Oncologist will prescribe sunitinib and monitor for toxicity during treatment

 If BCG is given locally no specimens need to be obtained at the Week 1 and Week 6 visits.

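### Section 7.1 times the primary response biopsy from enrollment, but the Schedule and study calendar place it after the sunitinib course and rest; a permitted 21-day start separates the two by 3 to 4 weeks

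*Combined protocol and SAP*

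**What the plan says.** Section 7.1 gives the response biopsy a clock that starts at enrollment: "All patients will be assessed at 3 months after enrollment with repeat bladder biopsy done at the study institution and urine cytology regardless of completion". The completion meant is that of drug treatment, and the reason given is usual care.

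Three other places describe the same assessment differently or leave the clock open:

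- **Protocol summary, Schedule.** Sunitinib is given "continuously for 28 days followed by a two week rest period. Patients will be reassessed with transurethral resection and urine cytology". This fixes the biopsy by treatment sequence and gives no week number.
- **Section 13.0, study calendar.** Weeks 1 to 6 are the first BCG course, sunitinib starts in Week 8, and the column headed "TURBT or bladder biopsy" stands at Week 14. The clock therefore starts with the first BCG week. No window is stated for that visit.
- **Sections 14.0 and 14.4.** Response is assessed at 3 months, with no statement of where the 3 months begin.

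The start of treatment can lag registration. Section 5.1 says "Following registration, patients should begin protocol treatment within 3 weeks", and adds "Issues that would cause treatment delays should be discussed with the Principal Investigator". The heading of Section 6.0 sets six weeks as the limit.

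Sections 14.4, 16.1 and 16.4.2 put every eligible patient with any sunitinib dose into the primary response analysis.

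**The concern.** The primary objective is complete response after BCG and a full sunitinib cycle of four weeks on and two weeks off. A biopsy dated from enrollment does not move when treatment starts late; a biopsy dated from first BCG, or from the end of the sunitinib rest, does. A late starter assessed under Section 7.1 would be judged on BCG plus part of the sunitinib course, and would still count towards the 16-of-24 and 25-of-36 rules.

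If sunitinib is active, such assessments would pull the observed response rate towards that of BCG alone. If it is inactive, the documents do not say how biopsy timing affects response. The date also steers treatment, because Section 7.1 offers a second full cycle to patients with residual non-muscle-invasive disease at this visit.

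**Working it through.** **Inputs.** Six weekly BCG doses, 14 days' rest, 28 days of sunitinib and 14 days' rest (Schedule; Sections 7.1 and 7.2). Biopsy at Week 14 from first BCG (Section 13.0). Biopsy at 3 months from enrollment (Section 7.1). Start within 21 days of registration (Section 5.1).

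**Assumptions.** Enrollment is taken as registration, and 3 months as 13 × 7 = 91 days. The BCG course ends either on the day of the sixth dose (5 × 7 = day 35 after the first) or after six full weeks (day 42). Results are given as first reading / second reading.

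**Step 1: reproduce the calendar's Week 14.** Day 0 is the first BCG dose.

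- Sunitinib starts on day 35 + 14 = 49, or 42 + 14 = 56. Day 49 opens Week 8 and day 56 closes it, as the calendar shows.
- The rest ends on day 49 + 28 + 14 = 91, or 56 + 28 + 14 = 98. Day 91 opens Week 14 and day 98 closes it.

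The Schedule and the calendar therefore agree with each other when no dose is held.

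**Step 2: compare with Section 7.1.** Let s be the days from registration to first BCG, and st the sunitinib start (49 or 56).

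- Calendar visit after registration = s + 91, or s + 98
- Gap = calendar visit − 91
- Sunitinib days by day 91 = min(28, max(0, 91 − s − st))
- Rest days by day 91 = min(14, max(0, 91 − s − st − 28))

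| s (days) | Calendar visit (day) | Gap (days) | Sunitinib days by day 91 | Rest days by day 91 |
|---|---|---|---|---|
| 0 | 91 / 98 | 0 / 7 | 28 / 28 | 14 / 7 |
| 7 | 98 / 105 | 7 / 14 | 28 / 28 | 7 / 0 |
| 14 | 105 / 112 | 14 / 21 | 28 / 21 | 0 / 0 |
| 21 | 112 / 119 | 21 / 28 | 21 / 14 | 0 / 0 |

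**Step 3: sensitivity to the length of 3 months.** Three calendar months run from 89 to 92 days. At s = 21, sunitinib days by the biopsy are 89 − 21 − 49 = 19 to 92 − 21 − 49 = 22 on the first reading, and 89 − 21 − 56 = 12 to 92 − 21 − 56 = 15 on the second. The gap runs from 112 − 92 = 20 to 119 − 89 = 30 days. The finding does not depend on the choice of 91.

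**Step 4: is a 21-day start compatible with the other limits?** Yes. Section 7.1 allows BCG within six weeks of the qualifying biopsy. A 21-day start meets this if the biopsy was no more than 42 − 21 = 21 days before registration.

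**Step 5: design figures.** An exact binomial calculation with the 16-of-24 and 25-of-36 rules gives early stopping 82.7% and false-positive error 4.93% at a true rate of 55%. At 75% it gives early stopping 12.1%, power 80.1% and false-negative error 19.9%. These match Section 16.1 (83%, 4.9%, 12%, 80%, 19.9%). The biopsy date does not enter the calculation.

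**The case against.** The best reply is that the calendar plainly governs. Section 9.0 says "Patients will be followed by study calendar". Section 7.1 itself adds "Patients completing at least one cycle of the study treatment will be assessed for primary and secondary endpoints where applicable". Section 7.2 describes a single six-week sunitinib cycle before responders are classified, and the primary objective in Section 1 includes the two weeks off drug. On this view, 3 months is only the nominal name of the Week 14 visit, and the clause about drug completion exists so that early stoppers are still biopsied. The trial recruits from one institution, and start delays go to the Principal Investigator.

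Much of this stands. It makes a mid-course biopsy less likely in practice, and it shows which rule should be kept. It does not remove the conflict: the Section 7.1 sentence covers all patients, names its starting point, is not limited to early stoppers, and is nowhere made subordinate to the calendar.

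A reader might be tempted to go further in three ways that the documents do not support:

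- **The six-week start limit as a worse case of dilution.** At s = 42, sunitinib days by day 91 are 91 − 42 − 49 = 0, or 0 on the second reading. Section 16.1 counts only patients with a sunitinib dose and replaces those removed before it, so this case does not establish dilution of the primary analysis.
- **The three-week and six-week start limits as contradictory.** They can be read as a target and an outer limit.
- **The ±3 weeks in Calendar 2 as a tolerance for this biopsy.** That window belongs to maintenance and surveillance. On the second reading the sunitinib rest ends only on day 98, so a window opening on day 91 would cut it short.

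**Conclusion.** The point holds as a conflict between stated rules, and it should be corrected. The rules agree within about a week for a prompt start. For a 21-day start they differ by 3 to 4 weeks, and a biopsy under Section 7.1 would follow 21 or 14 of 28 sunitinib days with no rest, in a patient who counts in the primary analysis.

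This rests on taking enrollment as registration; if enrollment is earlier, the gap is larger. It also assumes no held doses.

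A reader might infer that the reported response rate will be biased downwards, or that the trial's error rates are wrong. Neither follows. The documents give neither the share of late starters nor the response after a partial course, so the size of any bias cannot be derived. Alpha, power and cut-offs are unaffected. Confidence that the conflict would matter in practice is moderate, because most of the protocol already points to the calendar.

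**What to change.** - **Section 7.1:** replace the enrollment-based timing with study calendar Week 14, counted from first BCG, after the two-week sunitinib rest.
- **Early stoppers:** state that patients who stop study drug early still have the Week 14 biopsy, which preserves the purpose of the present sentence.
- **Sections 14.0 and 14.4:** define the 3-month response assessment as that visit. Recurrence-free and progression-free survival keep their enrollment origin.

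This is a change of wording, with no added visit or procedure, and no change to the sample size or decision rules. Its cost is clinical timing: for a 21-day starter the biopsy comes 3 to 4 weeks later than under a literal Section 7.1, so residual high-grade disease would be found that much later. That is the timing the calendar already prescribes. The change does not settle how far the visit may move after a held dose; the investigators would have to decide that.

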### 7.2 SUNITINIB

- Patients will receive a single 6 week cycle of sunitinib 2 weeks following a 6 week course of intravesical BCG. Complete responders as determined by no cancer on endoscopic biopsy

## [name], Phase II Study of BCG followed by Sunitinib for High risk NMIBC

AND no evidence of cancer on urine cytology will be placed on maintenance BCG by their treating physician as described in the study calendar.

- Patients with residual disease will receive a second course of treatment identical to the first cycle (BCG followed by sunitinib) assuming a normal MUGA scan (see study calendar).
- Patients demonstrating evidence of objective progression by endoscopic biopsy will be offered alternative treatments

## 8.0 CRITERIA FOR REMOVAL FROM STUDY:

8.1 Protocol therapy will be discontinued and patients will be removed from study based on any of the following criteria (Patients clinical course will be followed for two years.):

- Patients' wishes.
- Disease progression as documented by 3 month or 6 month bladder tumor biopsy documenting progression to muscle invasive bladder cancer.
- Clinician and patient determine that alternative treatment plan should be pursued. Reason for pursuing alternative therapy will be documented.
- Intercurrent illness that prevents further administration of treatment.
- Unacceptable adverse event(s) that may or may not be directly related to BCG and/or sunitinib but that in the judgment of the treating physician make it dangerous for the patient to be retreated.
- General or specific changes in the patient's condition that render the patient unacceptable for further treatment in the judgment of the investigator.

8.2 As an excessive rate of withdrawals can render the study un-interpretable, unnecessary withdrawal of patients should be avoided.

8.3 When a patient discontinues treatment early, the Investigator will make every effort to contact the patient and to perform a final evaluation. The reason(s) for withdrawal will also be recorded. The reason for terminating therapy should be clearly recorded.

## 9.0 DURATION OF FOLLOW-UP

- Patients will be followed by study calendar
- the clinical course of all patients will be followed for a total of 2 years following completion of 1st or 2nd induction course of the study therapy.

## 10.0 DOSING DELAYS/DOSE MODIFICATIONS

## 10.1 TICE BCG

### 10.1.1 DELAYS

- For patients experiencing bladder related symptoms, all attempts will be used to supportive care to have the patient complete a complete 6 week course at the full dose.
- Patients with gross hematuria and/or evidence of urinary tract infection during treatment as documented by urinalysis and/or confirmed by urine culture will be delayed administration of the dose by 1 week and restarted after confirming absence of gross hematuria and/or lack of nitrite positivity on dipstick urinalysis.
- Those patients with a greater than 3 week delay between doses during the 1st induction course will be removed from the study prior to initiation of sunitinib and be replaced with another eligible patient. Those unable to complete a 2nd induction course of BCG will be offered alternative therapy and followed for secondary endpoints where applicable.
  - Any patient with systemic infection caused by TICE BCG will be withdrawn from further BCG treatment. If this occurs during the first induction course, these subjects will be replaced, otherwise, patients will be offered alternative therapy and followed for applicable secondary endpoints.
  - Patients on maintenance BCG therapy will be given the full dose unless persistent urinary symptoms or systemic side effects (malaise, fever, fatigue) deter treatment. Dose reduction to -1 will be attempted first. Patients will be allowed to decrease dose to -2 if intolerance persists. Those patients who do not tolerate a dose of -2 during (see table in section 6.1) maintenance therapy will be withdrawn from further BCG administration and offered alternative treatment plan at the discretion of the treating clinician.

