## [name], Phase II Study of BCG followed by Sunitinib for High risk NMIBC

compared to endoscopic resection alone as well as intravesical chemotherapy with mitomycin, thiotapec, and other agent, BCG demonstrates superior delay in time to recurrence.[33, 34] However, delay in recurrence has not definitively translated into a change in overall survival or time to progression.[35]

In an effort to improve the long term effects of BCG, several groups have advocated maintenance BCG for those patients who respond to an initial or second induction course. Results of a randomized controlled study of BCG with or without maintenance therapy demonstrated increased time to disease recurrence compared to a single induction course (77 versus 36 months, log rank test p-value <0.001).[34]

Intravesical BCG is routinely used in Urologic practice and the safety and side effects are well established. The most frequent side effects of BCG include the development of lower urinary tract symptoms during treatment including urgency and frequency. In addition, patients may develop microscopic hematuria during BCG therapy.

[figure not shown]
Systemic symptoms may occur with BCG administration including fever, malaise, and fatigue. The most serious side effects related to BCG are infection. Up to 10 % of patients may develop urinary tract infection which is most commonly caused by coliform bacteria. However, local infection of the bladder and prostate may develop which can usually be managed by discontinuation of the BCG and treatment with fluoroquinolone antibiotics. Rare systemic infections related to BCG most commonly occur when BCG is delivered to patients with gross hematuria or following traumatic foley catheterization. This is managed by discontinuation of therapy and treatment with anti-tuberculosis agents in addition to fluoroquinolone antibiotics. This systemic infection may require hospitalization for management of symptoms and initiation of therapy.

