### 3.2 EXCLUSION CRITERIA

- 3.2.1. Patients with a prior history of radiation for bladder cancer
  - Patients with a prior history of radiation for prostate cancer are eligible for the study
- 3.2.2.  $\geq T2N0M0$  transitional cell carcinoma of the bladder on current pathology or in the past. Patients with a prior history of upper tract urothelial carcinoma are eligible for participation in the study as long as there is no evidence of disease for 6 months prior to study enrollment
- 3.2.3. Patients with other malignancies are eligible for enrollment in the study but should not be on active treatment for this malignancy within 12 months of study enrollment. Patients with prior history of local treatment for prostate cancer are eligible for participation in the study
- 3.2.4. Patients cannot have received Sunitinib or other anti-angiogenic therapy for at least 12 months prior to enrollment in the study
- 3.2.5. History of allergic reactions attributed to compounds of similar chemical or biologic composition to BCG and Sunitinib
  - Patients with prior systemic infection with BCG are not eligible for the study
  - Patients with prior intolerance to BCG may be considered
- 3.2.6. Major incisional surgery within 4 weeks of study enrollment
- 3.2.7. Bleeding diathesis or unresolved gross hematuria after bladder biopsy
- 3.2.8. Known HIV – positive patients may not participate. This is to avoid additional complications that immune suppression and HIV infection may cause due to treatment with BCG, which is a live attenuated bacteria that is known to cause systemic infection in patients who are immunocompromised.
- 3.2.9. Patients taking agents that result in immunosuppression are not eligible for the study due to the potential for the increased risk of systemic infection in those patients receiving BCG
- 3.2.10. Any of the following within the 6 months prior to study drug administration: myocardial infarction, severe/unstable angina, coronary/peripheral artery bypass graft, **symptomatic congestive heart failure (CHF)**, cerebrovascular accident or transient ischemic attack, or pulmonary embolism.
- 3.2.11. Ongoing cardiac dysrhythmias of NCI CTCAE grade  $\geq 2$ .

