#### *6.1.4 DOSE REDUCTIONS: Please refer to Section 11.*

### 6.1.5 SUPPORTIVE CARE GUIDELINES:

- Irritative bladder symptoms occur in 50% of patients
  - For patients with bothersome symptoms, medications such as pyridium, propantheline bromide, oxybutynin and acetaminophen can be used
- “Flu-like” symptoms (malaise, fever, chills)
  - Are related to the immune and hypersensitivity response and can be managed with ibuprofen, acetaminophen, and antihistamines
- Ocular symptoms (uveitis, conjunctivitis, iritis, keratitis, granulomatous choreoretinitis) alone or in combination with joint symptoms (arthritis, arthralgia), urinary symptoms, and/or skin rash have been reported. Patients positive for HLA-B27 appear to be at elevated risk
  - Dose reduction will be attempted
  - If persistent, BCG will be halted although patients will be allowed to continue to the Sunitinib portion of the study.
- Infection: Urinary tract infection, prostatitis, orchitis/epididymitis have all rarely been reported with BCG. Serious disseminated infections to the lung, liver, bone, bone marrow, kidney, and regional lymph nodes have been reported in case reports in the literature. Finally, sepsis has been reported with associated mortality.
- If a patient develops persistent fever ( $> 38.5$  C) or experiences an acute febrile illness consistent with BCG infection, BCG will be immediately discontinued and the patient will be evaluated for BCG infection
- Local infections may often be managed with discontinuation combined with a fluoroquinolone antibiotic such as ciprofloxacin or levofloxacin. However, rare cases of epididymitis and orchitis have not been successfully managed and may require antituberculosis therapy and/or orchiectomy
- More serious infections will be evaluated and might require one of the following actions:
  - Hospital admission with urine and blood cultures
  - Supportive therapy
  - Infectious disease physician consultation
  - Initiation of anti-tuberculosis therapy including isoniazid, rifampin, and/or ethambutol (not pyrazinamide)

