### 10.1.2 REDUCTION

- Intrapatient dose reduction by 1, and if needed 2- dose level(s) will be allowed (see Table below) depending on the type and severity of toxicity encountered provided that criteria for patient withdrawal from study treatment have not been met.
- All intra-patient dose reductions are relative to the lowest dose level of the current cycle.
- No more than 2 dose reductions are permitted in any patient. If further dose reduction is required, the patient must be removed from further BCG administration.
- The dosing period may be extended for BCG as outlined in section above
- The below table describes the recommended dose modifications for study treatment associated toxicity.

TABLE: DOSE MODIFICATION FOR BCG BASED ON TOXICITY AND GRADE

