# if BCG infection of grade 3 or 4 occurs during the 1st induction course, patients will be withdrawn from the study and replaced. Otherwise, patients will be offered alternative therapy at the discretion of the treating clinician and followed for appropriate endpoints.

### 10.2 SUNITINIB: In the event of any (CTC version 3) drug related grade 3 or 4 non-hematologic or

Toxicity	Grade 1	Grade 2	Grade 3	Grade 4
Irritative Bladder symptoms	Continue at the same dose level	Continue at the same dose level.	Dose reduction to -1. If Grade 3 toxicity persists, reduction to -2. Discontinuation will occur at the discretion of the treating clinician.	Dose reduction to -1. If Grade 4 toxicity persists, reduction to -2. Discontinuation will occur at the discretion of the treating clinician.
Fever, chills and "flu-like" symptoms	Continue at same dose level.	Continue at same dose level.	Dose reduction to -1. If Grade 3 toxicity persists, reduction to -2. Discontinuation will occur at the discretion of the treating clinician	Dose reduction to -1. If Grade 4 toxicity persists, reduction to -2. Discontinuation will occur at the discretion of the treating clinician
Occular symptoms +/- joint symptoms	Continue at the same dose level.	Continue at the same dose level.	Dose reduction to -1. If Grade 3 toxicity persists, reduction to -2. Discontinuation will occur at the discretion of the treating clinician	Dose reduction to -1. If Grade 4 toxicity persists, reduction to -2. Discontinuation will occur at the discretion of the treating clinician
Infection	Treat* and continue at same dose after resolution of symptoms within 2 weeks	Treat* and continue at same dose after resolution of infection within 2 weeks	Withdraw BCG treatment#	Withdraw BCG treatment#

grade 4 hematologic adverse event(s) drug should be held until the toxicity resolves to < grade 1 and then the drug should be restarted at -1 dose level (see 6.1).

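### The Infection row of the BCG dose-modification table (10.1.2) has no exception for systemic BCG infection of grade 1 or 2, which section 10.1.1 says ends BCG at any grade

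*Combined protocol and SAP*

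**What the plan says.** Section 10.1.1 (Delays) gives the rule for systemic infection: "Any patient with systemic infection caused by TICE BCG will be withdrawn from further BCG treatment". It names no grade. The sentence that follows it replaces the patient if the infection occurs in the first induction course. In later courses the patient is offered other therapy and followed for the applicable secondary endpoints.

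Section 10.1.2 (Reduction) introduces the table this way: "The below table describes the recommended dose modifications for study treatment associated toxicity". In the Infection row, the grade 1 cell reads "Treat* and continue at same dose after resolution of symptoms within 2 weeks" and the grade 2 cell reads "Treat* and continue at same dose after resolution of infection within 2 weeks". The grade 3 and grade 4 cells withdraw BCG. The row has two footnotes. The asterisk, attached to the word for treating, says that treatment depends on the type of infection. The # footnote, attached to the grade 3 and 4 cells, opens "if BCG infection of grade 3 or 4 occurs during the" and goes on to withdrawal from the study and replacement in the first induction course.

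Three other places deal with the same risk:

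- Section 2.3, on systemic infection: "This is managed by discontinuation of therapy and treatment with anti-tuberculosis agents in addition to fluoroquinolone antibiotics".
- Section 6.1.5, on persistent fever or an acute febrile illness that looks like BCG infection: "BCG will be immediately discontinued and the patient will be evaluated for BCG infection".
- Section 3.2.5, on entry to the study: "Patients with prior systemic infection with BCG are not eligible for the study".

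**The concern.** Two places in section 10 tell the clinician what to do with BCG after an infection. One acts on what the infection is, the other on how severe it is. For a systemic BCG infection graded 1 or 2 they point in opposite directions: stop for good, or resume at full strength once it has cleared.

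What is at stake is a further dose of a live organism for a patient who has already had a systemic infection from it, and whom section 3.2.5 would have refused at entry had that infection come before enrolment. A clinician with an infection to manage would naturally turn to a table arranged by toxicity and grade. The stop rule is less easy to find: it is a sub-item under a bullet on delays of more than 3 weeks, in a subsection headed as being about delays.

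**Working it through.** The protocol gives no figure on this point, so there is nothing to reproduce. The check is a comparison of texts, tracing one case through each: a systemic infection caused by TICE BCG, graded 1 or 2, that resolves within 2 weeks.

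1. **Section 10.1.1.** The trigger is systemic infection caused by TICE BCG, at any grade and in any course. Result: no more BCG, with replacement if in the first induction course.
2. **Table, grade 1 and 2 Infection cells.** The trigger is infection of that grade, of any type or cause. The condition is resolution within 2 weeks, of symptoms at grade 1 and of the infection at grade 2. Result: BCG continues at the same dose.
3. **Asterisk footnote.** It qualifies how the infection is treated. The rest of each cell, which continues BCG afterwards, has no qualifier. Result: the instruction in step 2 stands.
4. **# footnote.** It hangs on the grade 3 and 4 cells and names BCG infection of those grades. Result: it is silent at grades 1 and 2.
5. **Proviso in section 10.1.2 about withdrawal criteria.** It limits the permission to reduce the dose by one or two levels. The grade 1 and 2 cells order no reduction, so on its wording the proviso does not reach them.
6. **Section 6.1.5.** It stops BCG at once and calls for evaluation, but does not say whether BCG may resume after a BCG infection has been confirmed and has cleared. Result: it agrees with stopping and leaves the later step open.
7. **Sections 2.3 and 3.2.5.** Neither has a grade limit. Both agree with 10.1.1.

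Steps 1 and 2 give opposite answers for the same patient, and steps 3 to 5 supply no exception. Steps 6 and 7 show which answer was intended: the two table cells are out of line with the rest of the protocol.

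**How many patients.** The side-effect list in section 11.1 puts systemic infection in its rare group, at less than 1%. That figure covers all grades, whereas the conflict concerns grades 1 and 2 only. Section 15.0 names CTCAE version 3.0 for grading, but its infection grades are not reproduced. The share of systemic BCG infections that would be graded 1 or 2 therefore cannot be derived here. It could be zero, if such infections are always graded 3 or higher. For that reason no expected count is given.

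**The case against.** The strongest reply is that the protocol already settles the matter. Section 10.1.1 is mandatory, applies to every patient and is specific to systemic BCG infection. The table is general, is only recommended, and comes in the very next subsection. Sections 2.3, 3.2.5 and 6.1.5 all side with 10.1.1. Section 8.1 also removes any patient for whom the treating physician judges retreatment dangerous, and section 6.1.3 advises against antimicrobials during BCG, which would discourage giving BCG alongside treatment of the infection. Most of this stands, and a careful reader would follow 10.1.1. What remains is that no sentence gives 10.1.1 precedence, and the table gives the opposite instruction without pointing back to it.

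A second reply rests on the asterisk. If treatment depends on the type of infection, and section 2.3 counts stopping BCG as part of managing the systemic type, a reader could reach discontinuation through the footnote. That is possible, but the cell would then tell the clinician both to stop BCG and to continue it at the same dose. The footnote may raise doubt, but it does not state an exception.

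Third, the # footnote naturally names grades 3 and 4, because those are the cells it belongs to. It does not deny withdrawal or replacement at lower grades. This is fair: the footnote is incomplete beside 10.1.1 rather than contrary to it.

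A reader might also infer that a local urologist would work from the table alone and give BCG again. The documents do not support that as a prediction. Under section 6.1.2 local administration needs the principal investigator's approval, and local induction is checked against the study protocol, of which 10.1.1 is part.

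**Conclusion.** The inconsistency is real but narrow. For a systemic BCG infection of grade 1 or 2, section 10.1.1 ends BCG, while the table continues it after resolution within 2 weeks. Section 10.1.1 should be taken as governing, and the table should be brought into line with it.

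The size is small: few patients, possibly none. This rests on the listed rate of less than 1% for all grades and on an open question, namely whether a systemic BCG infection can be graded 1 or 2 at all.

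Two stronger readings should be set aside:

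- **That the protocol endorses giving BCG again after systemic infection.** It does not. Its mandatory rule and three other sections say the opposite.
- **That the conflict disturbs the primary analysis, because the two texts differ on who is replaced in the first induction course.** Under section 16.1, evaluable patients are those who take at least one dose of sunitinib, and those removed before then are replaced. The planned 24 and 36 patients, the response thresholds and the error rates stay as they are. At most, an individual patient would be replaced under one text and kept under the other, and nothing in the documents suggests a bias from this.

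The case for acting is patient safety, and the change is optional but worthwhile.

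**What to change.** Two edits to the BCG table in section 10.1.2, both applying the existing rule of 10.1.1:

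1. In the grade 1 and grade 2 Infection cells, add: 'except systemic BCG infection of any grade: withdraw BCG (see 10.1.1)#'.
2. Widen the opening of the # footnote to 'If systemic BCG infection of any grade, or BCG infection of grade 3 or 4,' and let it run on as now. Its second sentence already agrees with 10.1.1 for later courses and can stay.

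The other cells and section 10.1.1 need no change. The cost is one phrase in two cells and a longer opening to one footnote. It needs no new clinical decision and no extra patients, visits or analyses.
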